## 10 STATISTICAL CONSIDERATIONS

### 10.1 Study Hypotheses

This Phase 1, first-in-human study is not designed to test a formal null hypothesis. Rather, it is intended to obtain exploratory, initial data on the study product safety and effect of antigen dose and inclusion of the GLA-SE adjuvant on humoral immune responses to guide future dose selection.

### 10.2 Sample Size Considerations

This Phase 1 study is not designed for confirmatory testing but rather to detect AEs related to the study product. If an AE has a 20% chance of occurring after receiving one of the product formulations being tested, then there is an 87% probability that the event would be observed in one or more of the 9 subjects in that treatment group in this study. If the event has a 20% chance or higher of occurring in **any** of the product formulations being tested, then there is at >99% probability that the event would be observed in one or more of the 45 subjects in any treatment group in the study. The below table shows analogous probabilities for events with other frequencies.

Probability of event after receiving study product	Probability of observing event among 9 subjects	Probability of observing event among 45 subjects
0.01	0.086	0.364
0.05	0.370	0.901
0.10	0.613	0.991
0.15	0.768	0.999
0.20	0.866	>0.99
0.25	0.925	>0.99

### 10.3 Treatment Assignment Procedures

#### 10.3.1 Randomization Procedures

This is a non-randomized trial. Per ICH guideline E6: GCP, screening records will be kept at each participating VTEU site to document the reason why an individual was screened, but failed trial entry criteria. The reasons why individuals failed screening will be recorded in the Statistical Data Coordinating Center's (SDCC) Advantage eClinical Electronic Data Capture System.

---

Once consented and upon entry of demographic data and confirmation of eligibility for this trial, the subject will be enrolled. All subjects will receive three study product injections; the same study product formulation will be given to the subject for each study product injection. In the unlikely event that a subject withdraws prior to receiving the first injection, the subject will be replaced with a new subject who will be given the same treatment assignment.

### **10.3.2 Masking Procedures**

This is an open-label clinical trial.

Subjects, investigators, study personnel performing any study-related assessments following study vaccine administration are not blinded to study treatment. Laboratory personnel performing immunologic assays will receive samples blinded to subject ID number and sample visit number.

The SMC may receive data in aggregate and presented by Study Group.

## **10.4 Planned Interim Analyses**

Interim analyses will be used to terminate this trial in the event that unanticipated safety events deemed to be of sufficient concern require such action by the sponsor. These assessments will not be made on the basis of testing a formal statistical hypothesis; therefore, p-value adjustment will not be made to any analyses. A SMC will be convened by DMID to review study progress and participant, clinical, safety, reactogenicity and immunogenicity data as described in [Section 8.7](#)

To guide protocol development of future studies of the candidate vaccine, interim analyses of safety data and immunogenicity assays, including the IgG ELISA assay, will be performed at the discretion of the study team prior to completion of follow-up of all subjects. The interim immunogenicity analyses report(s) will include between-Group comparisons of those who received different Sm-p80 study product formulations and different schedules. The information from the report may be used in abstracts and scientific presentations and reports.

### **10.4.1 Interim Safety Review**

An interim safety review may include enrollment and demographic information, medical history, concomitant medications, physical assessments, dosing compliance, and solicited and unsolicited AE/SAEs. Additional data may be requested by the SMC, and interim statistical reports may be generated as deemed necessary and appropriate by DMID. The SMC may receive data in aggregate and presented by treatment arm. The SMC will meet and review this data at scheduled time points or ad hoc as needed during this trial as defined in the SMC charter. As an outcome of each review/meeting, the SMC will make a recommendation as to the advisability of proceeding

---

with study vaccinations (as applicable), and to continue, modify, or terminate this trial.

Additionally, this trial will be monitored to determine if any of the halting rules described in [Section 8.6](#) are met.

#### **10.4.2 Interim Immunogenicity or Efficacy Review**

Interim immunogenicity analyses of, for example, IgG ELISA responses will be performed for each Study Group, as the data is available for each study group. Depending on the timing of data availability, a report may cover one or more Study Groups. Immunogenicity reports will be provided by the SDCC to the DMID Scientific Lead and CPM, the IDCRC LOU representative(s), the study PI and investigators, and the SMC. Reports will include data summarized by Study Group. The data will be cleaned but not locked. These reports along with interim safety results may be presented in publications, or public forums and used by the product developers for internal decision-making.

### **10.5 Final Analysis Plan**

Analyses for this Phase 1 study will be descriptive and are exploratory rather than confirmatory in nature. Every attempt will be made to collect all planned measurements. Statistical adjustments for missing data are not planned, but sensitivity analyses may be performed if warranted.

An interim CSR will be completed when all primary and secondary endpoint data are available, received by the SDCC, cleaned, and locked. Exploratory endpoint data will be included in an addendum to the CSR once available, received by the SDCC, cleaned, and locked. Endpoint data may be included in publication of manuscript(s) or other reports.

Separate SAP documents (interim and addendum) will be generated that will contain the details of the final analyses that will be performed following database lock. This section outlines the major components of the final analyses.

#### **10.5.1 Analysis of Demographics**

Descriptive summaries of demographic variables, including age, sex, race, and ethnicity, will be summarized by study group. Numeric variables will be summarized by mean and standard deviation; categorical variables will be tabulated.

#### **10.5.2 Analysis of Safety Data**

All participants who received at least one vaccination will be included in safety summaries. Solicited and unsolicited events will be summarized graphically and numerically. Numbers and proportions of participants experiencing solicited systemic events will be summarized by

---

symptom, study group and maximum severity. Furthermore, proportions of participants experiencing systemic events will be summarized by study day, study group, and maximum severity. Solicited injection site events will be summarized in the same way as systemic solicited events.

Numbers and proportions of participants experiencing unsolicited AEs will be summarized by MedDRA System Organ Class and Preferred Term, study group, and maximum severity. Unsolicited AEs will also be summarized by relationship to study product, study group, and maximum severity.

Detailed listings of MAAEs, NOCMCs, PIMMCs, and all SAEs, will be presented, including the most recent dose number, number of days since most recent dose, relationship to study product, severity, outcome, MedDRA System Organ Class and Preferred Term, and study group.

Time trends of laboratory parameter values will be visualized with background shading indicating normal and graded ranges for that parameter.

### **10.5.3 Analysis of Immunogenicity Data**

Immunogenicity summaries will include all participants who received at least one study vaccination and contributed both pre- and at least one post-study vaccination blood sample for immunogenicity testing for which valid results were reported. Antibody levels will be summarized graphically and numerically. Individual time trends will be visualized as will reverse cumulative distribution plots. Numbers and proportions of participants with seroconversion, defined as a fourfold rise from baseline, will be presented along with 95% CIs by time point and study group. Statistical summaries will include geometric means, geometric mean fold-rise, mean, median, standard deviation, minimum, and maximum by time point and study group.

### **10.5.4 RNA-Seq Analysis**

For the transcriptomics exploratory analysis, sequencing quality will be inspected using FASTQC. RNA-Seq data will be pre-processed by removing adapters and low-quality reads, trimming low quality ends, and mapping sequences to the latest human reference genome using splice-aware alignment software such as *HISAT2*. Gene expression quantification will be carried out by using the *Subread* software [26] using the latest Ensembl gene model annotations as a reference. Systematic differences in sequence coverage between samples will be accounted for using the TMM method [31] as implemented in the *edgeR* R package. Principal component analysis, non-metric multidimensional scaling, and hierarchical clustering analysis will be used to identify potential global outliers and systematic batch effect. Negative binomial models as implemented in *edgeR* [28] will be used to identify genes for each dose group and post-

---

vaccination day that were differentially expressed compared to last vaccination: Days 8 and 29 vs. Day 1, and Day 36 vs. Day 29 for all study groups, Day 57 vs. Day 29, Day 64 vs. Day 57 for Groups A, B, D, and E, Day 187 vs. Day 180 for Group C. To control for testing multiple genes, the false-discovery rate based on the Benjamini-Hochberg procedure[32] as implemented in the *p.adjust* R function will be applied. The *pvclust* [33]R package will be used to identify co-expressed DE gene clusters. Mean cluster  $\log_2$  fold change time trends and associated 95% bootstrap confidence intervals (CIs) will be presented by group across post-vaccination days. To functionally characterize differently expressed genes, pathway enrichment analysis based on the latest MSigDB [34]and KEGG databases[35] as well as Blood Transcription Modules will be carried out using the implementation provided by the *goseq* R package [36]which accounts for RNA-Seq gene length bias. Pathway maps color-coded by treatment effect ( $\log_2$  fold change compared to pre-vaccination) will be visualized for significantly enriched KEGG pathways. Pathway enrichment trends by group across post-vaccination days will be visualized using bubble plots contrasting median pathway response with pathway enrichment as well as time trend plots of median pathway responses (based on median average  $\log_2$  fold changes of all pathway members) and associated 95% bootstrap CIs. Regularized linear and/or logistic regression analysis as implemented in the *glmnet* R package [37]will be utilized to identify gene expression changes that are predictive of antibody levels that provide protective efficacy *ex vivo* as measured using passive transfer. Cross-validation in combination with bootstrap resampling will be used to select optimal models and to assess robustness of variable selections. Please see the separate document “Statistical Analysis Plan” for additional information on exploratory RNA-Seq analyses.

---

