## 3 STUDY DESIGN, OBJECTIVES AND ENDPOINTS OR OUTCOME MEASURES

### 3.1 Study Design Description

This is a Phase 1, open-label, dose-escalation clinical trial to evaluate the safety, reactogenicity, and immunogenicity of the Sm-p80 + GLA-SE candidate schistosomiasis vaccine (SchistoShield®) in healthy adults 18 through 55 years of age. The Sm-p80 antigen is a recombinant protein produced in *E. coli* and GLA-SE is an immunological adjuvant.

Five treatment groups, each including nine subjects, will receive three intramuscular (IM) injections of 0.5 mL of the designated study product on either Days 1, 29, and 57 or on Days 1, 29, and 180 (Table 1). Group A (unadjuvanted comparator) will receive 100 µg Sm-p80 alone on Days 1, 29, and 57, Group B (low dose standard schedule) will receive 10 µg Sm-p80 + 5 µg GLA-SE on Days 1, 29 and 57, Group C (mid dose delayed booster) will receive 30 µg Sm-p80 + 5 µg GLA-SE on Days 1, 29 and 180, Group D (mid dose standard schedule) will receive 30 µg Sm-p80 + 5 µg GLA-SE on Days 1, 29, and 57, and Group E (high dose standard schedule) will receive 100 µg Sm-p80 + 5 µg GLA-SE on Days 1, 29 and 57. Dose escalation will proceed as described in the Protocol Summary.

Reactogenicity will be measured by the occurrence of solicited injection site and systemic reactions from the time of each study product injection through seven days after each study product injection. Unsolicited AEs of all severities, and concomitant medications, will be collected from the time of each study product injection through the next 28 days. During periods of follow-up outside of the 28-day post-vaccination interval, only SAEs, medically attended adverse events (MAAEs), new onset chronic medical conditions (NOCMCs), and potentially immune-mediated medical conditions (PIMMCs) will be collected. Clinical laboratory evaluations for safety will be performed on venous blood collected prior to, and approximately seven days after, each study vaccination.

Immunogenicity testing will include measuring titers of total IgG against the Sm-p80 protein by ELISA. Gene expression will be evaluated using RNA Seq analysis from whole blood.

For additional details on study procedures and evaluations and study schedule by study visits/days, see [Sections 6](#) and [7](#) and Table 8 and Table 9.

---

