### 3.3.3 Exploratory

- Identification and characterization of gene expression changes as measured using RNA-seq analysis from whole blood relative to last vaccination.
  - Days 8 and 29 vs. Day 1, and Day 36 vs. Day 29 for all study groups
  - Day 57 vs. Day 29, Day 64 vs. Day 57 for Groups A, B, D, and E
  - Day 187 vs. Day 180 for Group C
- Identification and characterization of gene expression changes as measured using RNA-Seq relative to last vaccination that correlate with peak Sm-p80 IgG antibody levels.
  - Days 8 and 29 vs. Day 1, and Day 36 vs. Day 29 for all study groups
  - Day 57 vs. Day 29, Day 64 vs. Day 57 for Groups A, B, D, and E
  - Day 187 vs. Day 180 for Group C

---

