### 7.2.2      **Research Assays**

The research assays to be performed for the immunologic endpoints are specified below.

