### **7.2.2.2 RNA-Seq**

RNA Sequencing (RNA-Seq) will be performed by Novogene from the whole blood PAXgene tubes that will be shipped from TTUHSC. Novogene will perform total RNA extraction, RNA quantification and qualification, library preparation, Illumina whole-transcriptome sequencing, and raw data quality checking. Novogene will transfer the raw FASTQ files to Emmes. Emmes will perform RNA-Seq data analyses, including pre-alignment sequence quality control, reference alignment, post-alignment quality control, gene expression quantification, differential gene expression analyses, gene cluster and pathway analyses, as well as predictive modeling (see Section 10.5.4).

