### **9.3 Consent for Secondary Research Use of Stored Specimens and Data**

#### **9.3.1 Secondary Use of Stored Specimens and Data**

Secondary Human Subject Research is the re-use of identifiable data or identifiable biospecimens that were collected from some other “primary” or “initial” activity, such as the data and samples collected in this protocol. This section will detail the samples and data

---

available for secondary research. Any use of the secondary sample or data, however, will be presented in a separate protocol and require separate IRB approval.

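### The RNA-Seq prediction model in Protocol 10.5.4 has an outcome defined by passive transfer, which the supplied documents do not describe and which does not match the peak-IgG exploratory endpoint

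*Protocol*

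**What the plan says.** Protocol 3.3.3 lists two exploratory endpoints. The first is gene expression change after vaccination. The second is expression change "relative to last vaccination that correlate with peak Sm-p80 IgG antibody levels". SAP 3.2.3 repeats both and mentions neither protection nor passive transfer.

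Protocol 10.5.4 describes the analysis. Its last modelling step uses regularized linear and/or logistic regression (glmnet) to find expression changes "predictive of antibody levels that provide protective efficacy" ex vivo, "as measured using passive transfer".

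On measurement, Protocol 7.2.2 opens with "The research assays to be performed for the immunologic endpoints are specified below". Two assays follow: the anti-Sm-p80 IgG ELISA (7.2.2.1) and RNA-Seq (7.2.2.2). Protocol 3.1 says the same of the antibody work: "Immunogenicity testing will include measuring titers of total IgG against the Sm-p80 protein by ELISA".

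Both documents defer detail. Protocol 10.5 announces separate interim and addendum SAPs, and SAP 4.5.2 places RNA-Seq analysis in a separate SAP, to be reported in a CSR addendum.

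**The concern.** A prediction model needs an outcome that the study observes. The outcome in 10.5.4 requires either a passive-transfer result for each subject or a titer that passive transfer has shown to be protective. The documents supply neither. The model is also the only step in 10.5.4 that relates expression to antibody, so its wording decides whether the second exploratory endpoint has an analysis at all.

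Two things are at stake. First, allowing logistic regression without a cutoff leaves a dichotomized outcome undefined. Titers will be known early: SAP 6.2 and 6.6.2 provide interim ELISA reports by group to the investigators and the sponsor, while the exploratory results come in a later addendum. Second, genes selected by a model described in these terms could be reported as predictors of protection, which this trial does not measure.

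**Working it through.** There is no figure to reproduce, so the check sets the relevant places side by side.

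1. **Outcome required.** Protocol 10.5.4: antibody levels, qualified by protection in passive transfer.
2. **Where passive transfer appears.** Only in that sentence of 10.5.4. It is absent from the endpoints, the assay section, the schedules of events and the SAP.
3. **What is collected.** Protocol Tables 8 and 9 (SAP Tables 2 and 3) provide for safety bloods, serum for antibody assays and secondary research, PBMC for secondary research, and whole blood for gene expression. None is assigned to a functional or protection assay.
4. **Whether stored samples fill the gap.** Not within this protocol. Section 9.3.1 states: "Any use of the secondary sample or data, however, will be presented in a separate protocol". Section 9.3.2 bars evaluation of the serum and PBMC sent to one laboratory until after final database lock and approval.
5. **Whether a threshold is given.** No protective titer appears in either document. The only dichotomy defined for antibody is seroconversion, a fourfold rise from baseline (Protocol 3.3.2, SAP 3.3).
6. **Endpoint the model should serve.** Peak Sm-p80 IgG (Protocol 3.3.3, SAP 3.2.3).
7. **Whether another step serves it.** The remaining steps of 10.5.4 are differential expression with edgeR, clustering with pvclust and pathway enrichment with goseq. They address the first exploratory endpoint. SAP section 11 covers ELISA summaries only, and SAP section 12 is marked not applicable.

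Steps 1 to 5 show that the outcome as worded cannot be derived from the trial's data. Steps 6 and 7 show that, in these documents, the peak-IgG endpoint has no analysis under its own name.

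Peak IgG can be derived, but *peak* is not defined, and the definition matters because sampling differs by group. SAP 11.1.1 gives these ELISA days after baseline:

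| Sample | Groups A, B, D, E | Group C |
|---|---|---|
| 7 and 28 days after dose 1 | 8, 29 | 8, 29 |
| 7 and 28 days after dose 2 | 36, 57 | 36, 57 |
| Before dose 3, separate draw | none | 180 |
| 7 and 28 days after dose 3 | 64, 85 | 187, 208 |
| 124 days after dose 3 | 181 | 304 |

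A maximum over every available draw would use 2 + 2 + 2 + 1 = 7 samples in Groups A, B, D and E, and 7 + 1 = 8 in Group C. Restricting it to the 7- and 28-day samples gives 3 × 2 = 6 in every group, matched on time since dose.

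**The case against.** The strongest reply is that the defect is narrower than it looks, and much of that reply stands.

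- **A reader might infer that the model cannot be run at all, or that no subject will have an outcome.** The documents do not support this. The regression target is antibody level, and passive-transfer protection qualifies it. Antibody level is measured by ELISA at every immunogenicity visit, and 10.5.4 allows linear regression. Without the qualifier, the model has data.
- **A reader might infer that the peak-IgG endpoint has no analysis anywhere.** This cannot be shown. The separate RNA-Seq SAP was not supplied and may specify a peak-IgG model. The absence is established only for the protocol and the supplied SAP.
- **A reader might infer that a protective cutoff is to be chosen from the trial's own titers.** Neither document proposes that. The wording leaves room for it, which is reason to close the gap but not evidence of intent.

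It can also be said that the clause may be left over from a wider exploratory programme: SAP section 15 records that exploratory endpoints other than RNA-Seq were removed. That is a plausible inference, and it would make this a clean-up. It does not remove the inconsistency, because the clause is in the current protocol and Section 7.2.2.2 refers predictive modelling to it.

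Finally, the analyses are descriptive and exploratory, with no formal hypothesis. That limits the consequence, but the endpoint and its analysis should still agree.

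**Conclusion.** Wrong as written, for an exploratory endpoint only. The outcome worded in Protocol 10.5.4 rests on a measurement that neither supplied document describes, and it does not match the endpoint stated in both. The missing data concern the passive-transfer qualifier, not antibody level.

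The effect reaches one of the two exploratory endpoints. Primary safety and secondary IgG analyses do not use this model and are unaffected.

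The conclusion assumes that Protocol 7.2.2 lists all the research assays and that no protective titer is to be taken from a source outside the documents. A peak-IgG model in the unseen RNA-Seq SAP would settle the missing-analysis part, but 10.5.4 would still need to be reconciled with 3.3.3.

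**What to change.** In Protocol 10.5.4, and consistently in the RNA-Seq SAP:

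1. Replace the passive-transfer clause with log-transformed peak anti-Sm-p80 total IgG ELISA titer as the primary outcome of a linear glmnet model.
2. Define peak by visit and group before the RNA-Seq analysis. One workable rule is the maximum over the 7- and 28-day post-dose samples, taking Days 187 and 208 for Group C's third dose and Days 64 and 85 for the other groups. State how missed visits are handled.
3. If logistic regression is kept, use the fourfold-rise seroconversion already defined, not a protective cutoff set after titers are seen.
4. If the sponsor does intend a passive-transfer outcome, add it as a defined assay, with its samples, timing and any threshold.

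Items 1 to 3 take a few sentences and use ELISA data already scheduled. Only item 4 would add laboratory work.

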## 11 SOURCE DOCUMENTS AND ACCESS TO SOURCE DATA/DOCUMENTS

Each participating site will maintain appropriate medical and research records in compliance with ICH E6, Section 4.9 and regulatory and institutional requirements for the protection of confidentiality of subjects. Each site will permit authorized representatives of the DMID, its designees, and appropriate regulatory agencies to examine (and when required by applicable law, to copy) clinical records for the purposes of quality assurance reviews, audits, and evaluation of the study safety and progress. These representatives will be permitted access to all source data and source documents, which include, but are not limited to, hospital records, clinical and office charts, laboratory notes, memoranda, subjects' memory aid or evaluation checklists, pharmacy dispensing records, recorded data from automated instruments, copies or transcriptions certified after verification as being accurate and complete, microfiches, photographic negatives, microfilm or magnetic media, x-rays, and subject files and records kept at the pharmacy, at the laboratories, and medico-technical departments involved in the clinical trial.

This study uses direct data entry for the participating clinic site and the eCRFs serve as the source documents for data collected.

Subjects will use a web-based electronic Memory Aid (e-Memory aid), or paper Memory Aid if internet access is not available. Data entered by subjects into the e-Memory Aid are stored in the data system for clinic staff review during scheduled visits. The e-Memory Aid is not considered source data. After clinic staff review and save the data, the data will be entered into Advantage eClinical as source.

---

